Commencement of DIALIVE treatment session i.e. connection of patient to the Prismaflex machine = time point 0, can occur at any time before the end of study Day 1 subject to availability of all relevant information required for treatment to commence. All blood samples should be measured from this time point. Any pre samples required should be taken just before connection.

Nuts and bolts of DIALIVE Treatment: a ready reference

-Before starting treatment

The patient to be moved to an intensive care unit or similar once randomised to DIALIVE. Appropriate monitoring needs to be instituted including the following:

- Insertion of an arterial line for continuous invasive blood pressure monitoring and blood sampling
- Insertion of a vascular catheter for DIALIVE treatment
- Insertion of a central venous catheter for prompt treatment with vasopressors if required (Lines should be inserted under USS guidance. Correction of clotting abnormalities, if any, should follow local protocols. The line positions should be confirmed through appropriate means; e.g. CXR for neck lines).

 * NB: Majority of ACLF grade 3 patients are likely to be already in the ICU with the above monitoring in situ.

Additional tests (Baseline samples for FBC, U/E, LFT, coagulation, septic screen will already have been collected to check eligibility) prior to commencing DIALIVE therapy will be done:

Arterial blood gas analysis

- Haemolysis screen (FBC including reticulocyte count, blood film, unconjugated and conjugated bilirubin, LDH, haptoglobin, urinary free haemoglobin) – to be performed only on D1, before and after therapy
- DIC screen, if clinically indicated
- And, Endotoxin Activity Assay (EAA) analysis (start of day 1, 2 and 3)
- Blood to be collected as part of biobank samples.(start of day 1, 2 and 3)

Fluid pre-loading of up to 500mls over 1-2 hours is implemented, the volume and speed of fluid therapy to be determined on a clinical basis, and the choice of fluid would preferably be albumin (4.5 or 5% solution as per local availability).

- during dialysis session

- Anticoagulation with unfractionated heparin and/or prostacycline analogues (the dose as per local protocols)
- Blood flow rates on DIALIVE device to be started at 50 mls/min and increased gradually over 1-2 hours to up
 to a maximum of 250 mls/min

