6. STATISTICAL CONSIDERATIONS

An independent statistician will be responsible for all statistical aspects of the investigation.

All statistical analyses will be carried out on the safety population, defined as the subset of randomised patients who receive at least one treatment. No imputation of missing values will be implemented. Only available data will be analysed. In addition, a sensitivity analysis will be carried out to check the main safety results using SAE-data of all evaluable patients, defined as all those patients who received standard of care or those who received the correct dialysis treatment cycle.

Due to the nature of the study all statistical analyses will be descriptive. The categorical variables will be summarised by means of the count and percentages corresponding to each variable category, while continuous variable will be summarised by the mean and Standard Deviation of each distribution or the median and min-max values in case of those variables non-normally distributed.

Clinical Investigation Plan CIP YAQ-002 Version: 7.0 10 October 20	19
--	----

For each treatment arm, treatment-emergent AEs, SAEs, SADEs, ADEs, USADEs and DDs will be summarised by organ system and treatment causality. The number and percentage of patients discontinuing the study due to AEs, SAEs, SADEs or other stopping criteria confirmed by the DSMB (withdrawal of patient consent; development of septic shock; progression to ACLF Grade 3b or more; disseminated Intravascular coagulation; unanticipated serious adverse device effects, device deficiencies, or in the opinion of the PI, the treatment is unsafe to continue) will be summarised by treatment arm.

Secondary and exploratory parameters (changes from baseline at each study visit) will be descriptively analysed by treatment arm by means of the appropriate statistics.

Statistical analyses of safety data will be run when each study cohort is completed (minimally one week FU) and the corresponding results will be communicated to the DSMB.

Special interim data extraction required to comply with the EU ALIVER program.

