12.5. Foreseeable adverse events and anticipated adverse device effects

Listed below are known complications associated with liver disease

- Gastrointestinal bleeding
- Spontaneous Bacterial Peritonitis (SBP)
- Hepatic Encephalopathy (HE)
- Hypotension
- Septic shock
- Respiratory failure
- Cardiovascular failure
- Renal insufficiency
- Hepatorenal syndrome
- Death

Any existing condition will be recorded at baseline during screening. Further events relating to an existing condition will not be recorded as an AE unless in the opinion of the PI, the condition has worsened since baseline. All AEs will be recorded from the point of consent and reported to the Sponsor in accordance with section 13.2.

During initial human dialysis sessions, and subsequent DSMB reviews, the following (potential) device related SAEs were observed; these were incorporated in the latest version of the Investigator Brochure:

- Hypotension: this resulted in a series of recommendations to follow during the DIALIVE treatment (see §3.2 of CIP)
- Higher then expected albumin drop during dialysis led to additional in vitro tests supporting the need to administer
 g albumin every hour of dialysis (see §3.4 of CIP and §8.1 of IB)
- Anemia was observed in one patient, requiring blood cell pack administration to restore the hemoglobin level. (see page §3.2 of CIP and §9.1, 11.2 and 12.3i of IB)

Reference is made to section 3.2 of this document, where also the anticipated events related to extracorporeal circulation and to kidney dialysis are summarized

Clinical Investigation Plan CIP YAQ-002 Version: 7.0 10 0	October 2019
---	--------------

12.6. Emergency contact details for reporting serious adverse events, serious adverse device effects and device deficiencies.

All SAEs and USADEs will be reported to the CRO via the eCRF. In the event access to the eCRF is not available, paper SAE forms will be completed by the site and emailed to:

[contact]

or via fax ([contact]).

Please refer to Appendix 6 for Country Specific Safety Reporting.

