B) upon review of the safety aspects observed in cohort 2 of the study.

[figure not shown]
14 subjects have been enrolled to the study so far; 8 DIALIVE and 6 SOC, 2 of 8 DIALIVE patients were non-evaluable as per the study protocol since they failed to complete the minimum treatment required for analysis. Overall, with the exception of the 2 non-evaluable DIALIVE patients, the intervention seems to be safe and is well tolerated with some expected adverse events such as a degree of hypotension, mild platelet consumption and potential complications related to the lines being used to deliver the treatment. The two deaths in the DIALIVE arm, both occurring within 24-36 hours of treatment having been commenced, appear to be multifactorial including progression of the disease itself and the learning curve of the sites using such treatment for the first time thus sometime not realising the nuances of such treatment. Following the recommendations made at the interim DSMB meeting whereby a standard document was created to capture these nuances for ready reference to the site teams, the three DIALIVE patients treated since then had a very stable treatment course.

We therefore, based on the evidence provided to us by the central study team and the sponsor, feel reasonably confident that the study should continue to the next cohort as and when practical.

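### The by-arm adverse event summary is limited to treatment-emergent events, a filter that on its ordinary meaning omits the DIALIVE preparation period and has no starting point in the SOC arm

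*Protocol*

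**What the plan says.** Section 6 sets the by-arm safety tables: "For each treatment arm, treatment-emergent AEs, SAEs, SADEs, ADEs, USADEs and DDs will be summarised by organ system and treatment causality". The synopsis has the same rule. Neither place says when an event becomes treatment-emergent.

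A synopsis footnote defines one treatment as exposure to the DIALIVE of any length. No treatment start is defined for SOC.

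Section 2.2 gives the order of events in the DIALIVE arm. Under its heading for steps before treatment it lists:
- transfer: "The patient to be moved to an intensive care unit or similar once randomised to DIALIVE"
- an arterial line, a central venous catheter and "Insertion of a vascular catheter for DIALIVE treatment"
- fluid pre-loading over one to two hours

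The session itself then begins: "Commencement of DIALIVE treatment session i.e. connection of patient to the Prismaflex machine = time point 0". The use stated for that time point is sampling: "All blood samples should be measured from this time point".

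The collection of events is wider than the summary. Section 12.5 says: "All AEs will be recorded from the point of consent". Section 12.3.3 separates serious device effects due to DIALIVE from those due to investigation procedures. Section 5.1.5 promises a full report of every SAE. The primary endpoint (section 5.1.2) counts patients with an SAE from study Day 1 to Day 10.

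**The concern.** The primary objective is the safety of DIALIVE compared with SOC. Allocation to DIALIVE brings preparatory procedures that carry their own risk. Section 3.2 lists blood loss from venous cannulation among the risks, and the Data Safety Monitoring Board's (DSMB) review after cohort 2 (Appendix 7) mentions "potential complications related to the lines being used to deliver the treatment".

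A treatment-emergent filter normally counts events from the start of treatment. Here the start can fall as late as the end of Day 1, after the lines and the pre-load. Harms from the preparation would then be missing from the DIALIVE summary, although they follow from the allocation. In the SOC arm the same filter has nothing to attach to. The two columns of the table would not cover the same period, and the omission would tend to favour the device.

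**Working it through.** The plan states no figure that could be reproduced. The sample size is set arbitrarily and no hypothesis is tested (section 5.3.7). The check is therefore a reading of the rules against each other, followed by a calculation for scale only.

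**Step 1. Which rule captures which event.** Inputs: randomisation is Day 0; the first session must start before the end of Day 1 (section 2.2); the primary window is Day 1 to Day 10 (section 5.1.2); when dialysis takes place on Day 0, its clinical data are entered as Day 1 (section 7.1.1); a DIALIVE patient not started by the end of Day 1 is a screen failure (section 2.2) and is replaced (section 5.1.7); the safety population requires at least one treatment (section 6).

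| Serious preparation event in the DIALIVE arm | Treatment-emergent, ordinary meaning | Primary SAE count |
|---|---|---|
| Day 1, before connection on Day 1 | No | Yes |
| Day 0, before connection on Day 0 | No | Yes, if entered as Day 1 under section 7.1.1 |
| Day 0, before connection on Day 1 | No | No |
| Patient never connected | No | No: outside the safety population |

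The by-arm summary misses all four rows. Among connected patients, the primary endpoint misses only the third. The fourth row arises from the population rule, not from the word treatment-emergent, but the affected patients are lost from the same tables.

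**Step 2. The SOC arm.** With treatment defined as DIALIVE exposure, an SOC patient has no first treatment. Any start used for SOC must be supplied from elsewhere, so the stated filter cannot be applied in the same way to both arms.

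**Step 3. Scale.** Five cohorts with 3 DIALIVE patients each give 5 × 3 = 15 evaluable patients.
- One patient whose only SAE is omitted: 1/15 = 6.7 percentage points.
- The main analysis uses treated patients, who may number more than 15. If the 17% dropout in section 5.1.7 applied to this arm and all dropouts had been connected, the number would be 15/0.83 ≈ 18, and one patient would be 1/18 = 5.6 points.

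**Step 4. Chance of at least one such patient.** The documents give no rate, so the per-patient rate p is an assumption. The formula is 1 − (1 − p)^15:
- p = 1%: 14%
- p = 2%: 26%
- p = 5%: 54%
- p = 10%: 79%

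The width of this range shows that the size cannot be derived from the documents.

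**The case against.** The strongest reply is that the protocol does not define treatment-emergent, and that the definition usually belongs in the statistical analysis plan, which is not at hand. A reader might infer that the protocol starts adverse event counting at connection. It does not say so: time point 0 is tied to the session and to blood samples. The omission follows from the ordinary meaning of the term together with the footnote on treatment. This part of the reply stands.

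It can also be said that section 6 uses the word treatment loosely. Read strictly, its safety population would contain no SOC patients, which cannot be intended. This weakens any strict connection-based reading. It also shows that the section needs a start that works in both arms.

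A reader might further infer that these harms disappear from safety reporting or from the primary endpoint. They do not. Most pre-connection events in connected patients fall inside the Day 1 to Day 10 window, every SAE is to be reported in full, and the DSMB has commented on line complications. Its comment does not say that these occurred before connection.

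Nor do the documents support the view that only DIALIVE patients meet such risks. Section 2.2 expects most grade 3 patients to have the monitoring already in place, and SOC may include fluids, albumin and dialysis.

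What remains is that an analysis plan can define the term, but the protocol has chosen a filter that has no natural start in one of the two arms being compared.

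**Conclusion.** The point holds for the by-arm safety summary. As worded, it would leave out serious complications between randomisation and connection in the DIALIVE arm, and it gives the SOC arm no matching start. This rests on the ordinary meaning of treatment-emergent, since the protocol gives no other.

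The effect on the primary endpoint is smaller. Among connected patients it is limited to Day 0 events before a Day 1 connection. Patients never connected are lost through the screen-failure and replacement rules.

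The size is unknown. One treated patient is worth at most about 6.7 points of the DIALIVE SAE percentage, less if more than 15 are treated, and nothing if that patient has another SAE that is counted. The documents support neither a specific event rate nor a claim that the corresponding number in SOC is zero. The change is still worth making, because the comparison of harms is the purpose of the trial and the remedy is cheap.

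**What to change.** In section 6 and the synopsis:
- Replace treatment-emergent with a rule that works in both arms: events with onset or worsening after randomisation.
- State that the primary SAE count also starts at randomisation (Day 0), and align section 5.1.2.
- In the DIALIVE arm, show on separate lines the events from randomisation to connection and the procedure-related events (lines, pre-load). Include in these lines the randomised patients who were never connected.

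The cost is a change of wording and a few table rows. Section 12.5 already requires recording from consent. The schedules in section 5.4 mark the first adverse event assessment at Day 1, so the sponsor should confirm that Day 0 events are being captured. The downside is that the DIALIVE SAE figure may be slightly less favourable.

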5.1.2 Primary Endpoints

The goal is to evaluate the percentage of subjects who experience at least one (1) serious adverse event (SAE) between study Day 1 and Day 10; especially the incidence rate of SAE between the study groups occurring in the period of Day 1 to Day 10.

The percentage of subjects who discontinued DIALIVE due to a serious adverse device event (SADE) between Day 1 (first day of treatment) and Day 10 (DIALIVE arm only)¹⁰.

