5.2. Investigational device exposure

For the randomization an Interactive Wireless Randomization System (IWRS) is used, which is linked to the study data base. Randomization is automatically assigned through the IWRS system. Patients are randomised to either the DIALIVE or SOC arm in a 1:1 ratio.

¹¹ The prismaflex platform will be provided by Yaqrit to those sites that do not have access to such haemofiltration machines. The machine will remain the property of Yaqrit Ltd during and after the study. A mainenance agreement in such circumstances will be established with each institution.

Patients will be assigned into five (5) Cohorts. Each cohort will consist of six (6) patients (3 DIALIVE: 3 SOC). If there are dropouts in any of the following cohorts during the study period, patients will be replaced in each of the cohorts described below to reach the appropriate number of 6 evaluable patients in each cohort.

Cohort 1: including 3 control and 3 DIALIVE treated patients. Cohort 2: including 3 control and 3 DIALIVE treated patients. Cohort 3: including 3 control and 3 DIALIVE treated patients. Cohort 4: including 3 control and 3 DIALIVE treated patients. Cohort 5: including 3 control and 3 DIALIVE treated patients.

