5.3.4. Point of enrolment

Patients will be recruited through in-patient wards across multiple European centres. Approximately one (1) patient every four (4) months per centre will be recruited with an estimated three (3) patients per centre in total, although competitive recruitment will be utilised. This recruitment strategy is based upon the data accumulated during the performance of the CANONIC study [5].

Following consent and confirmation of eligibility, patients will be randomised electronically via the eCRF . The site will be issued with the subject ID number and informed of their treatment arm. Patients will be deemed enrolled at the point of randomization (Day 0).

5.3.5. Total expected duration of the clinical investigation.

The total duration of the study will be approximately 39 months.

5.3.6. Expected duration of each subject's participation.

After signing the Informed Consent, the patient can be screened for compliance with the in/exclusion criteria for up to 3 days. Patients from cohort 1, 2 and 3 are followed for 28 days, those from cohort 4 and 5 for 90 days.

Patients will be randomized on study day 0 followed by a maximum treatment window period of 10 days (DIALIVE arm). All patients will be intensively followed during the initial 28 days post-randomization and complete the study after completion of study day 28 (cohort 1, 2 and 3) or day 90 (cohort 4 and 5)...

5.3.7. Number of subjects included in the clinical investigation.

30 evaluable subjects will be randomised to receive either standard of care (SOC) or treatment with DIALIVE (1:1 randomisation).

As this is a first-in-man trial, and no hypothesis is to be tested, the sample size is arbitrarily set to obtain adequate information in a small patient population. This reduces the total number of patients exposed to potential study related risks while allowing the investigators to learn maximally from this potential treatment for ACLF-patients for which no alternative

Clinical Investigation Plan	CIP YAQ-002	Version: 7.0 10 October 2019
-----------------------------	-------------	------------------------------

treatment exists and the Data Safety Monitoring Board to make appropriate decisions on study (dis)continuation by comparing occurrence of adverse events between control and treatment arms in each of the 5 cohorts of patients.

5.3.8. Estimated time needed to select this number (i.e. enrolment/recruitment period).

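### Section 6 lets the cohort safety analysis go to the DSMB after one week, before the primary SAE window ends on Day 10 and possibly before the cohort can be confirmed complete

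*Protocol*

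**What the plan says.** **Timing of the cohort analysis.** Section 6: "Statistical analyses of safety data will be run when each study cohort is completed (minimally one week FU". The DSMB receives these results. The start of the one-week clock is not defined. The synopsis carries the same sentence with no minimum follow-up at all.

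**Primary endpoint.** Section 5.1.2 counts patients with at least one "serious adverse event (SAE) between study Day 1 and Day 10".

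**Treatment window.** In Section 5.3.6, randomisation on Day 0 is "followed by a maximum treatment window period of 10 days (DIALIVE arm").

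**Cohort completion.** Section 5.2: "Each cohort will consist of six (6) patients (3 DIALIVE: 3 SOC"), with dropouts replaced until six patients are evaluable. Section 5.1.7 counts an SOC patient who dies within 10 days of randomisation as a dropout to be replaced. Section 2.2 requires a DIALIVE patient to complete one successful three-day cycle within the 10-day window to be evaluable.

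**Use of the review.** Section 5.3.7 says the DSMB decides on continuation "by comparing occurrence of adverse events between control and treatment arms in each of the 5 cohorts of patients". Appendix 7 records that after cohort 1 the DSMB approved enrolment of six more patients. The synopsis bases the extension to ACLF grade 3a on a favourable DSMB report.

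**The concern.** The trial's main safety question is fixed at Day 10, but the analysis that informs the decision to continue may be run at about Day 7. The patients most likely to be cut short are the last to enter the cohort. A DIALIVE patient whose cycle restarted after a failed session may still be under treatment at that point.

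The rule also sits badly with the definition of a completed cohort. The analysis is triggered by completion, but whether the last patients count towards the six may not be settled until Day 10.

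Two features of the data flow add to this. The schedules in Section 5.4 place adverse event assessments on Days 1, 3, 5 and 10 (also Day 2 for DIALIVE), so the last scheduled assessment before a one-week cut is Day 5. Section 12.2 gives sites up to three calendar days to report an SAE, so a one-week cut can miss events that have already happened.

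At stake is the completeness of the safety picture before more patients are exposed in a first-in-man study that Section 5.5 rates as high risk.

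**Working it through.** **1. The plan's own figure.** 5 cohorts × 6 patients = 30, or 15 per arm. This matches Section 5.3.7. The protocol gives no power, effect size or expected SAE rate, so there is nothing further to reproduce.

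**2. Length of the gap.** One week ends on Day 7 if counted from randomisation (Day 0), or on Day 8 if counted from Day 1. The primary window ends on Day 10.
- 10 − 7 = 3 days unobserved
- 10 − 8 = 2 days unobserved

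**3. When a cohort can be confirmed complete.**
- An SOC patient is known not to be a 10-day death only after 10 days.
- A DIALIVE patient who completes a cycle on Days 1 to 3 is evaluable early. One whose cycle restarts may not be settled until Day 10.
- So if the last patient is SOC, or is DIALIVE with a restarted cycle, six evaluable patients cannot be confirmed at one week.

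**4. Deaths falling in the gap.** Input: 28-day mortality m of 22% (ACLF grade 1) and 32% (grade 2), cited in Section 2.7. Assumption: constant hazard. Risk of death by day d = 1 − (1 − m)^(d/28).

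| m | By Day 7 | By Day 8 | By Day 10 | Missed, Day 7 cut | Missed, Day 8 cut |
|---|---|---|---|---|---|
| 22% | 6.0% | 6.9% | 8.5% | 2.5 points | 1.6 points |
| 32% | 9.2% | 10.4% | 12.9% | 3.7 points | 2.4 points |

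Section 2.7 also cites 78% for grade 3 as a whole. It is not used because the trial admits only grade 3a, for which the protocol gives no separate figure.

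**5. First SAEs falling in the gap.** The protocol gives no SAE rate, so the 10-day risk P is assumed to be 30%, 50% or 70%, again with constant hazard. Risk by day d = 1 − (1 − P)^(d/10).

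| P | By Day 7 | Missed, Day 7 cut | By Day 8 | Missed, Day 8 cut |
|---|---|---|---|---|
| 30% | 22.1% | 7.9 points | 24.8% | 5.2 points |
| 50% | 38.4% | 11.6 points | 42.6% | 7.4 points |
| 70% | 56.9% | 13.1 points | 61.8% | 8.2 points |

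**6. How many patients are affected.** Thirty evaluable patients over about 39 months (Sections 5.3.5 and 5.3.7) is one per 39 / 30 = 1.3 months. Typically only the last patient of a cohort would be short of Day 10, or the last two if enrolment clusters.

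**The case against.** **One week is a floor with an undefined start.** If it is counted from the end of a cycle given on Days 1 to 3, it ends at about Day 10 and the gap closes. This stands as an ambiguity. It does not rescue the rule, because SOC patients have no cycle to count from and nothing in the text excludes counting from Day 0 or Day 1.

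**The evaluability rules themselves push completion towards Day 10.** That is fair, and in practice a cohort may often be declared complete later than one week. But the stated minimum is then either inoperative or in conflict with those rules, and the text should be reconciled.

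**Late events are not lost.** Sites report SAEs within three calendar days. Section 14 requires the sponsor to suspend the study on suspicion of unacceptable risk and to refer the information to the DSMB. The final analysis is unaffected. All of this stands and limits the size of the point.

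**The constant hazard may not hold.** Appendix 7 places both DIALIVE deaths reported there within 24 to 36 hours of starting treatment. That favours early events, but two deaths do not show that later SAEs are absent.

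**A stronger reading that the documents do not support.** From Section 5.3.7 a reader might infer that each continuation decision rests on three patients against three, and so cannot tell the arms apart. That sentence explains the sample size and is not a decision rule. Section 12.3.3 has the DSMB reviewing all safety data at time points set in its charter. The synopsis cites a review of 12 patients, and Appendix 7 a second review of 14 (8 DIALIVE, 6 SOC). The charter is not shown. The synopsis plans no statistical tests, so a p-value for a single cohort is a poor yardstick. Only a wording mismatch remains.

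**Conclusion.** The timing point holds. As written, Section 6 permits a DSMB analysis two to three days before the primary SAE window closes, and possibly before the cohort can be confirmed complete.

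The effect is modest and confined to the most recently enrolled patients. For a patient cut at Day 7 it is about 2.5 to 3.7 percentage points of death risk, given a constant hazard and 22% to 32% 28-day mortality. A Day 8 cut gives 1.6 to 2.4 points. For first SAEs the gap is larger, 5.2 to 13.1 points, but it rests wholly on assumed rates.

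A reader might restate the Day 7 figures as 29% of the deaths by Day 10 (2.5 / 8.5, or 3.7 / 12.9). That is a share within an affected patient's own 10-day risk. It does not mean that 29% of a cohort's deaths go unseen.

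The documents do not show that any past review was run too early. The finding concerns what the text allows. It is a cheap improvement to the safety review and leaves the final analysis as it is.

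**What to change.** **Main change.** In Section 6, replace the one-week minimum with: *the cohort safety analysis is run when every randomised patient of the cohort has completed Day 10, died or withdrawn consent*. Put the same condition in the synopsis, which now has none. This also removes the undefined clock and agrees with the evaluability rules in Sections 2.2, 5.1.7 and 5.2.

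**Secondary wording.** In Section 5.3.7, state that each DSMB review shows the arms cumulatively over all randomised patients to date, with the current cohort as a listing. This brings the section into line with Section 12.3.3, the synopsis footnote and Appendix 7. If the DSMB charter already says so, a cross-reference is enough.

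**Cost.** About two to three days' wait per cohort, so at most 10 to 15 days over five cohorts in a study of about 39 months. No new data collection is needed: Day 10 is already a scheduled visit, and excluded patients and those with an incomplete cycle are already followed for 28 days.
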